### **9.20.4 Subject Chooses to Exit (i.e., Revokes Consent)**

A subject can withdraw from the study at any time. If the subject wishes to exit from the study (i.e. the subject revokes consent), the study site is required to document the reason for exit on the Exit CRF. In addition, study sites shall follow the regulations set forth by the IRB. Reason for exit must be documented.

### **9.20.5 Investigator Withdraws Subject**

No subjects should be withdrawn by investigators unless compelling medical justification is present. It is recommended investigators discuss any withdrawals with the study team prior to withdrawing subjects. If an Investigator Withdrawal is necessary, the reason for withdrawal must be documented.

## **10.0 Risks and Benefits**

### **10.1 Potential Risks**

The potential risks associated with the investigational TMVR procedure are similar to the risks of cardiac surgery and mitral valve replacement. These risks may include, but are not limited to, the following risks:

- Death
- Cardiac damage or perforation, cardiac tamponade or pericardial effusion
- Coronary artery perforation, spasm, occlusion or obstruction
- Heart rhythm disturbances (e.g., atrial fibrillation, cardiac arrest)
- Conduction system disturbances (e.g., atrioventricular node block, left-bundle branch block, asystole), which may require a permanent pacemaker
- Aortic valve dysfunction (e.g., regurgitation or stenosis)
- Myocardial infarction, ischemia or angina
- Reduced cardiac function or continuing or worsening heart failure
- Stroke or transient ischemic attack (TIA)
- Encephalopathy / neurological deficit
- Renal insufficiency or failure (possibly requiring dialysis)
- Pulmonary complications (e.g., pulmonary congestion, hypertension, thromboembolism, dyspnea, respiratory failure, atelectasis, pneumonia)
- Surgical incision site complications (e.g., infection, inflammation, bleeding, hemothorax, hematoma, pain, irreversible nerve injury, wound dehiscence)
- Bleeding (possibly requiring a transfusion or other intervention)
- Emboli (air, thrombus)
- Infection (e.g., at incision sites, endocarditis, septicemia)
- Viral infection including Bovine Spongiform Encephalopathy (BSE)
- Blood abnormality (e.g., coagulopathy, hemolysis, anemia)
- Allergic or drug reaction (e.g., to anesthetic, contrast, Heparin, protamine, nickel alloy, latex)
- Esophageal complications due to transesophageal echocardiography (e.g., irritation, perforation, stricture)
- Tracheal complications due to intubation (e.g., irritation, perforation, dysphagia)

# The Early Feasibility Study of the Intrepid™ TMVR Transseptal System Clinical Investigation Plan

Version 4.0

Page 44 of 102

Medtronic

- Vascular access site complications (e.g., trauma, dissection, perforation, infection, inflammation, pain, bleeding, hematoma, pseudoaneurysm, irreversible nerve injury, compartment syndrome, arteriovenous fistula, stenosis)
- Aortic complications (for example, trauma, dissection, perforation, tears, aneurysm, pseudoaneurysm, or occlusion)
- Other systemic effects or symptoms (e.g., abnormal lab values, electrolyte imbalance, fever, hyperthermia, hypotension, hypertension, syncope, nausea, vomiting, edema, deep vein thrombosis, pleural effusion, lymphatic complications, urinary tract infection, multi-system organ failure, gastrointestinal bleeding, ischemia or infarction)
- Valve implant dysfunction (e.g., fracture, bending, under-expansion, suture breaks, calcification, pannus, thrombus, inflammation, stenosis, leaflet wear, tear, prolapse, retraction, poor valve coaptation, leaks, regurgitation, mal-sizing [prosthesis-patient mismatch])

The risks of the investigational TMVR procedure are similar to the surgical risks listed above; however, some may be increased with the TMVR procedure or implant. For example, the risks of cardiac damage may be increased by the TMVR delivery procedure, and the risk of valve implant dysfunction (as compared to surgical replacement valves) has not yet been established.

In addition to the risks listed above, the potential risks associated with the TMVR procedure and the Intrepid TMVR System may include, but are not limited to, the following risks:

- Valve implant detachment, migration, malposition, and/or incorrect sizing
- Injury to mitral valve apparatus complicating or preventing later surgical repair/replacement
- Left ventricular outflow tract (LVOT) obstruction
- Emergent surgical or transcatheter intervention (for example, coronary artery bypass, heart valve replacement or repair, transcatheter valve explant, percutaneous coronary intervention [PCI], balloon valvuloplasty, transcatheter valve or component retrieval)
- Failure to deliver the bioprosthetic to the intended site
- Failure to retrieve the system components
- Delivery system component embolization
- Delivery system thrombosis
- Prolonged cardiopulmonary bypass
- Prolonged ventilation, anesthesia, and/or procedure time
- Radiation skin burn or tissue reaction
- ASD with or without intervention
- Deep venous thrombosis (DVT)

*Medtronic Business Restricted*

**CONFIDENTIAL**

056-F275, vC Clinical Investigation Plan Template

- Dislodgement of previously implanted devices (e.g., Dislodgement of lead in patient with pre-existing permanent pacemaker, CRT-P, CRT-D or implantable defibrillator (ICD))
- Edema
- Gastrointestinal bleeding or infarction
- Hypotension/hypertension
- Lymphatic complications
- Mesenteric ischemia
- Mitral stenosis
- Multisystem organ failure
- Nausea/vomiting
- Peripheral ischemia
- Respiratory failure/atelectasis/pneumonia
- Urinary tract infection
- Vessel spasm
- Worsening heart failure

The likelihood of these risks is unknown, as this is the initial introduction of the investigational TMVR system into a human population. However, bench-top testing and animal studies have demonstrated that the TMVR procedure can safely and reliably result in stable positioning of The Intrepid TMVR implant and the desired improvement in hemodynamic performance.

There may be other, as yet unknown, complications that may occur as a result of this procedure. If these or any of the above complications occur, they may lead to repeat or prolonged hospitalization, repeat procedures, emergency surgery, other emergency procedures, or in rare cases, death. The study doctor and/or his research staff will make every effort to minimize additional risks.

## 10.2 Risk Minimization

The potential risks associated with the Intrepid™ TMVR System were identified and have been mitigated to the extent possible. Any potential risks associated with this study are further minimized by selecting qualified investigators and training study personnel on the CIP.

Medtronic has also attempted to minimize risk to subjects implementing a DMC to review safety issues as part of the study.

In addition, investigators will be actively involved in the implantation and follow-up of the subjects implanted with the Intrepid™ TMVR Systems.

Risks will be minimized by careful assessment of each subject prior to, during, and after implant of the Intrepid™ TMVR valve. Prior to implant, it is recommended subjects undergo a complete physical evaluation.

Medtronic has further minimized the possibility of risks by performing required laboratory and pre- clinical testing prior to this early feasibility study, implementing quality control measures into production processes, providing guidelines for subject selection and evaluation, and providing adequate instructions and labeling.

After implantation, subjects in this early feasibility study will be followed at regular intervals to monitor the condition of the implanted system. At each protocol required follow-up, the investigator must evaluate the Intrepid™ TMVR valve via TTE to verify appropriate valve function and to assess any adverse events.

## 10.3 Potential Benefits

Subjects who are eligible for this study suffer from moderate-severe or severe, symptomatic mitral regurgitation that requires definitive treatment. A participant may benefit from replacement of the mitral valve for treatment of mitral regurgitation. The potential benefits may include a reduction of mitral regurgitation and the possible health improvements and/or symptom relief associated with that reduction in mitral regurgitation.

There may be no direct benefit associated to participation in this trial, but the information obtained during this trial will be used scientifically to help physicians understand the implications of transcatheter treatment of the patient's mitral regurgitation.

## 10.4 Risk-Benefit Rationale

This early feasibility study will enroll only patients with moderate-severe or severe, symptomatic mitral regurgitation, who are ineligible for conventional mitral valve surgery. These patients, nevertheless, require treatment. This less invasive TMVR procedure may provide an alternative mitral valve replacement for patients for whom conventional surgery is not an option.

Transfemoral transseptal access may also mitigate procedural complications compared to transapical access from the TMVR procedure.

The human clinical experience, to date, has demonstrated successful implantation of the Intrepid TMVR system, proper TMVR function, and elimination of mitral regurgitation, warranting continued study in additional patients, as proposed in this study. The potential benefit of a less invasive transseptal procedure to reduce their mitral regurgitation is considered to outweigh the risks from a MVR surgical procedure or a transcatheter valve replacement via transapical approach.

The investigational plan is specifically designed to manage and minimize risks through careful patient selection, thorough training of investigators, adherence to the pre-determined time points to assess subject clinical status and regular clinical monitoring visits by Sponsor appointed monitoring personnel.

Study subjects will be exposed to the procedural and device risks associated with TMVR, as well as the study specific risks listed in [Section 10.1](#). However, evidence from the scientific literature

*Medtronic Business Restricted*

**CONFIDENTIAL**

056-F275, vC Clinical Investigation Plan Template

indicates subjects with moderate-to-severe or severe mitral regurgitation who do not receive therapy are exposed to the serious risks associated with their disease including worsening heart failure, irreversible ventricular functional impairment, and death.

While the Intrepid TMVR System is a novel device, based on the results of the Pilot Study and the benefits observed by relieving mitral regurgitation in other transcatheter mitral valve repair and replacement trials, it is expected that these benefits will be conferred to the study subjects in the Mitral Early Feasibility Study, and that the benefit of mitral regurgitation reduction will outweigh the risks of intervention.

In addition, an independent DMC will monitor safety of the subjects throughout the trial. Therefore, the risk/benefit ratio for the study is justified.

## 10.5 Risk Determination

The devices used in this study are considered significant risk per 21 CFR 812.

## **11.0 Adverse Events and Device Deficiencies**

### **11.1 Adverse Events**

Adverse Event (AE) definitions are provided in Section 11.4, Table 11-1. All subject AE information will be collected throughout the study duration, starting at the time of enrollment.

Reporting of these events to Medtronic will occur on an AE Form. Each event must be reported separately. Documented pre-existing conditions are not considered AEs unless the nature or severity of the condition has worsened.

For AEs that require immediate reporting (see Section 11.5, Table 11-3), initial reporting may be done on the CRF by completing as much information as possible. The completed AE CRF must be submitted to Medtronic as soon as possible.

Any medication/treatment associated with the treatment of an AE must be reported. Subject deaths are also required to be reported.

### **11.2 Device Deficiency**

Device deficiency information will be collected throughout the trial and reported to Medtronic. Device deficiencies that led to an AE are reported on the AE CRF. Device deficiencies that did not lead to an AE are to be reported on a Device Deficiency CRF (one for each device deficiency).

Device deficiencies will be assessed for SADE potential. Device deficiencies that did not lead to an adverse event but might have led to a SADE if:

- a suitable action had not been taken, or
- an intervention had not been made, or
- circumstances had been less fortunate,

Device deficiencies are to be reported to Medtronic as soon as possible, but no later than three (3) working days after the investigator first learns of the event.

### **11.3 Processing Updates and Resolution**

For any changes in status of a previously reported adverse event or DD (i.e. change in actions taken, change in outcome, change in relatedness), information needs to be updated on, or added to the original AE or DD form. All AEs must be followed until the AE has been resolved, is unresolved with no further actions planned, the subject dies or exits the study, or until study closure, whichever occurs first.

At the time of study exit, all collected adverse events that are unresolved must be reviewed and an update to the original AE must be reported.

## 11.4 Definitions/Classifications

The definitions to be applied for the purposes of reporting adverse events are provided in [Table 11-1](#).

**Table 11-1: Adverse Event and Device Deficiency Definitions and Reporting Requirements**

Event Type	Definition
Adverse Event (AE)  (ISO14155:2020 3.2)	
Any untoward medical occurrence, unintended disease or injury, or untoward clinical signs (including abnormal laboratory findings) in subjects, users or other parties, whether or not related to the investigational medical device and whether anticipated or unanticipated.
 
This definition includes events related to the investigational medical device or the comparator.
 
NOTE: This definition includes events related to the procedures involved. For users or other persons, this definition is restricted to events related to investigational medical devices or comparators.

Serious Adverse Event  (SAE) (ISO14155:2020 3.45)	
Adverse event that led to any of the following:
 
 
• death,
 
• serious deterioration in the health of the subject, users or other persons as defined by one or more of the following:           
 
1. life-threatening illness or injury, or
 
2. a permanent impairment of a body structure or a body function, including chronic diseases, or
 
3. in-patient or prolonged hospitalization, or
 
4. medical or surgical intervention to prevent life-threatening illness or injury or permanent impairment to a body structure or a body function,
 
 
 
• foetal distress, foetal death or a congenital abnormality or birth defect including physical or mental impairment
 
 
NOTE: Planned hospitalization for a pre-existing condition, or a procedure required by the CIP, without serious deterioration in health, is not considered a serious adverse event.
 
*The interpretation of Seriousness will exclude certain interventions considered standard of care during hospitalization (e.g., IV hydration, certain medications delivered intravenously due to available intravenous access or NPO (nothing by mouth) status, and the delivery of electrolytes to maintain electrolyte balance or to address mild electrolyte depletion). Any non-oral medication or fluid delivery used to treat an acute physical decompensation/deterioration episode or to otherwise resuscitate a subject will be considered serious by definition in that it prevents a permanent impairment of a body structure or deterioration of the health of a subject.

# The Early Feasibility Study of the Intrepid™ TMVR Transseptal System Clinical Investigation Plan

Version 4.0

Page 50 of 102

Medtronic

**Table 11-1: Adverse Event and Device Deficiency Definitions and Reporting Requirements**

Event Type	Definition
Adverse Device Effect (ADE) (ISO14155: 2020 3.1)	Adverse event related to the use of an investigational medical device. Note: This definition includes adverse events resulting from insufficient or inadequate instructions for use, deployment, implantation, installation, or operation or any malfunction of the investigational medical device. Note: this definition includes any event resulting from use error or from intentional misuse of the investigation medical device. Note: this includes 'comparator' if the comparator is a medical device.
Serious Adverse Device Effect (SADE) (ISO14155: 2020 3.44)	Adverse device effect that has resulted in any of the consequences characteristic of a serious adverse event.
Unanticipated Adverse Device Effect (UADE) (21 CFR 812.3)	Any serious adverse effect on health or safety or any life-threatening problem or death caused by, or associated with, a device, if that effect, problem, or death was not previously identified in nature, severity, or degree of incidence in the investigational plan or application (including a supplementary plan or application), or any other unanticipated serious problem associated with a device that relates to the rights, safety, or welfare of subjects.
Unanticipated Serious Adverse Device Effect (USADE) (ISO14155: 2020 3.51)	Serious adverse device effect (SADE) which by its nature, incidence, severity or outcome has not been identified in the current risk assessment.P Note: Anticipated serious adverse device effect (ASADE) is an effect which by its nature, incidence, severity or outcome has been identified in the risk assessment.
Device Deficiency (ISO 14155 : 2020 3.19)	Inadequacy of a medical device with respect to its identity, quality, durability, reliability, usability, safety or performance. Note: Includes malfunctions, user errors, and inadequacy in the information supplied by the manufacturer including labelling. Note: This definition includes device deficiencies related to the investigational medical device or the comparator
Serious Health Threat (ISO 14155: 2020 3.46)	A signal from any adverse event or device deficiency that indicates an imminent risk of death or a serious deterioration in the health in subjects, users or other persons, and that requires prompt remedial action for other subjects, users or other persons. Note: This would include events that are of significant and unexpected nature such that they become alarming as a potential serious health hazard or possibility of

Unavoidable events are conditions which do not fulfill the definition of an Adverse Event, such as those medical occurrences, clinical signs (including abnormal laboratory findings), diseases or injuries that are not untoward in nature, specifically, those resulting from the intended injury such as the index procedure. The events listed in [Table 11-2](#) are expected for patients undergoing the Index Procedure, and do not need to be reported as an AE unless they occur outside of the stated timeframe, are otherwise considered to be an AE according to the treating investigator or are suspected or confirmed to be device-related.

*Medtronic Business Restricted*

**CONFIDENTIAL**

056-F275, vC Clinical Investigation Plan Template

# The Early Feasibility Study of the Intrepid™ TMVR Transseptal System Clinical Investigation Plan

Version 4.0

Page 51 of 102

Medtronic

**Table 11-2: Non-Reportable Medical Occurrences Associated with the Index Procedure**

Event	Timeframe (hours) from the Index Procedure
Short transient episode of arrhythmias or conduction disturbances (including ventricular fibrillation) during index procedure	0
Confusion, anxiety and/or disorientation (other than TIA/stroke) starting within 48 hours with or without medical intervention	120 (5 days)
Temporary change in mental status (other than TIA/stroke) not requiring additional medical interventions or new medical assessments (eg, CT)	72
Dizziness and/or lightheadedness with or without treatment	24
Headache with or without treatment	72
Sleep problems or insomnia with or without treatment	120 (5 days)
Mild dyspnea or cough with or without treatment	72
Oxygen supply after extubation / “forced breathing therapy”	48
Diarrhea with or without treatment	48
Obstipation / Constipation with or without treatment	72
Anesthesia-related nausea and/or vomiting with or without treatment	24
Low-grade fever (<101.3°F or <38.5°C) without confirmed infection	48
Low body temperature	6
Pain (eg, back, shoulder) related to laying on the procedure table with or without treatment	72
Incisional pain (pain at access site) with or without standard treatment and patient not returning to clinic to have additional treatment	No time limit
Pain in throat and/or trachea due to intubation	72
Stress hyperglycemia	72
Mild to moderate bruising or ecchymosis	168 (7 days)
Atelectasis / Pleural Effusion not requiring punctuation	168 (7 days)
Edema resulting in weight increase up to 4 kg / 9lbs from baseline	68 (7 days)

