## Arrhythmias and Conduction System Disturbances

For emerging mitral valve procedures in which the frequency of major arrhythmias and conduction system disturbances is unknown, continuous rhythm monitoring for at least 48 h in the post-procedural period is recommended to maximize the detection of arrhythmias and conduction system disturbances.

Data elements to be collected for all patients should include:

- I. Baseline conduction abnormalities, paroxysmal or permanent atrial fibrillation (or flutter), ventricular arrhythmias, and the presence of permanent pacemaker and implantable defibrillators\*
- II. Procedure-related new or worsened cardiac conduction disturbance (including first-, second- [Mobitz I or Mobitz II], or third-degree AV block; incomplete and complete right bundle branch block; intraventricular conduction delay; left bundle branch block; left anterior fascicular block; or left posterior fascicular block, including heart block) requiring a permanent pacemaker implant; each subclassified as persistent or transient
- III. New-onset atrial fibrillation (or flutter)†
- IV. New-onset ventricular tachycardia or fibrillation
- V. Pacemaker or defibrillator lead dislodgement

Arrhythmias and conduction system disturbances are subclassified according to:

- I. The occurrence of hemodynamic instability
- II. Need for therapy including electrical/pharmacological cardioversion or initiation of a new medication (oral anticoagulation, rhythm, or rate control therapy)
- III. Need for new permanent pacemaker and/or defibrillator implantation, including the indication(s) and the number of days post-implant. For patients with defibrillators, the number of appropriate and

\* The type of permanent pacemaker should be recorded (e.g., single vs. dual chamber, biventricular).

† Which lasts sufficiently long to be recorded on a 12-lead electrocardiogram, or at least 30 s on a rhythm strip.

AV = atrioventricular

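### Serious ventricular fibrillation attributed to the delivery procedure is left to investigator discretion by the non-reportable list and may not reach the primary safety endpoint

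*Combined protocol and SAP*

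**What the plan says.** All references are to the EFS CIP unless stated otherwise.

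- **Table 11-2** lists as non-reportable: "Short transient episode of arrhythmias or conduction disturbances (including ventricular fibrillation) during index procedure". The timeframe is 0 hours, so only the procedure itself is covered. No duration is given for a short transient episode, and nothing is said about treatment or haemodynamic effect.
- **Section 11.4**, in the paragraph introducing that table, says "Unavoidable events are conditions which do not fulfill the definition of an Adverse Event". Listed events need no AE report unless they fall outside the timeframe, or "are otherwise considered to be an AE according to the treating investigator or are suspected or confirmed to be device-related".
- **Table 11-1** makes an AE serious if it led to death or life-threatening illness, or to "medical or surgical intervention to prevent life-threatening illness or injury or permanent impairment to a body structure or a body function". Its note adds that non-oral medication or fluid used for an acute decompensation or "to otherwise resuscitate a subject will be considered serious by definition".
- **Appendix 17.1.5** has the lead-in "Data elements to be collected for all patients should include", and item IV of its list is "New-onset ventricular tachycardia or fibrillation".
- **Sections 4.2.1 and 13.0** set the primary safety endpoint as SAEs related to the implant, its delivery or the device, through 30 days. **Sections 5.0 and 12.1** base safety endpoint results on CEC adjudication.

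**The concern.** The primary objective (Section 4.1.1) is the nature, severity and frequency of complications of delivering and implanting the device. VF during delivery is such a complication and can be lethal. Section 10.1 itself names rhythm disturbances, including cardiac arrest, among the risks. Several milder rows of Table 11-2 apply only if no further intervention was needed, no drainage was required, or no infection was confirmed. The VF row has no such condition.

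The endpoint reaches events related to implant or delivery as well as to the device, but the exception that makes reporting mandatory names only the device. If some serious VF is never entered as an AE, the reported rate is too low and nothing in the tables would show it.

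**Working it through.** The plan states no figure on this point, so there is none to reproduce. The check is a comparison of the rules, followed by arithmetic for scale.

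**1. Can an episode covered by the row be serious?** Yes. VF that is life-threatening, or is ended by an intervention to prevent life-threatening injury, fits Table 11-1, and resuscitation with non-oral drugs or fluids is serious by definition. A short episode can meet these criteria because the row does not limit treatment. A brief self-terminating episode need not meet any of them.

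**2. What do the exceptions restore?** Section 6.1 makes the delivery system and loading system part of the investigational system, and Table 11-1 counts events from inadequate deployment or implantation as device effects. Table 11-4 classifies relatedness to the TMVR procedure separately from the bioprosthesis, delivery catheter and loading system. For short, serious VF during the procedure this gives:

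| Attribution | Investigator considers it an AE? | Reported under 11.4? |
|---|---|---|
| Suspected or confirmed related to valve, delivery system or loading system | Either | Yes |
| Delivery procedure only | Yes | Yes |
| Delivery procedure only | No | No exception applies |

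The last row is the gap. The investigator's judgement is also not neutral, because the same paragraph has just said that listed events are not AEs. That judgement is made at up to 15 sites.

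**3. Is there another route to the CEC?** Section 12.1 describes CEC adjudication and sponsor safety review of events, and Section 12.3 has the monitoring committee review SAEs. None describes a route for an occurrence never entered as an AE.

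**4. Scale.** Sample size is up to 45, approved in increments of 15 (Section 8.1). Assume the endpoint is summarised as the proportion of subjects with at least one event. One omitted subject with no other qualifying SAE lowers it by 1/n:

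- 1/45 = 2.2 points
- 1/30 = 3.3 points
- 1/15 = 6.7 points

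With assumed counts and exact (Clopper-Pearson) 95% intervals:

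| Reported | Restored | Result |
|---|---|---|
| 5/45 | 0 | 11.1% (3.7 to 24.1) |
| 5/45 | 1 | 6/45 = 13.3% (5.1 to 26.8) |
| 5/45 | 3 | 8/45 = 17.8% (8.0 to 32.1) |
| 9/45 | 0 | 20.0% (9.6 to 34.6) |
| 9/45 | 3 | 12/45 = 26.7% (14.6 to 41.9) |

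The chance of at least one omission in 45 subjects is 1 − (1 − p)^45, where p is the proportion of subjects with serious VF that goes unreported. For assumed p of 1%, 2%, 5% and 10% it is 36%, 60%, 90% and 99%.

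The EFS CIP plans frequencies and percentages only (Section 13.1). The attached SAP plans exact intervals, but for the transapical pilot study CIP-1403, so the intervals here are illustrative.

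**The case against.** The strongest reply is that listing expected intraprocedural occurrences is a deliberate convention and that the exceptions already do most of the work. Suspicion alone is enough to make device-related VF reportable, and the device includes the delivery system. That stands. A reader might infer that all delivery-related VF drops out of the endpoint; Section 11.4, read with Section 6.1 and Table 11-1, does not support that.

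Three further points stand in part.

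- **Seriousness.** A reader might infer that every intraprocedural VF is an SAE. The documents make it depend on course and treatment. Consequences such as death or shock are not on the list and remain reportable.
- **Data collection.** A reader might infer that Appendix 17.1.5 obliges sites to complete an AE form for VF, or that VF goes unrecorded. The appendix says should, names no form, and Table 11-2 waives only AE reporting. The case report forms are not in the documents, so non-collection is not shown. But a procedural data field would not by itself bring the event to the CEC.
- **Scope of the endpoint.** The endpoint wording does not name the procedure, so one can argue that VF attributed only to the procedure lies outside it. The wording does name delivery alongside the device, however, and Section 9.17 bases the safety assessment on relatedness to the implant and index procedure. The pilot study's SAP (Section 7.9.1) counts SAEs related to the TMVR device or procedure for its similar endpoint. The EFS documents leave this unsettled, which is itself a reason to clarify.

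It is also true that the study has no pass or fail criterion (Section 13.1), so no decision threshold moves, and that each subject's data are reviewed individually (Section 13.0).

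**Conclusion.** The gap is real but bounded. It concerns short, serious VF during the index procedure that is attributed to the delivery procedure, is not suspected to be device-related, and is not called an AE by the investigator. Such an event can be left out of CEC adjudication and the primary endpoint without breaching the protocol.

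The size per omitted subject is 2.2 points at 45 subjects and 6.7 at 15, provided that subject has no other qualifying SAE. How many subjects would be affected cannot be stated, because the documents give no VF rate; the counts and probabilities above rest on assumed values. In a descriptive study whose primary aim is complication frequency, the change is worthwhile. The gap does not make the endpoint unusable.

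**What to change.** Reconcile Table 11-2, Section 11.4, Table 11-1 and Appendix 17.1.5 with two edits.

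1. In the Table 11-2 row, change the word including to excluding in the parenthesis on ventricular fibrillation. Deleting the parenthesis would not be enough, since VF would still fall under arrhythmias.
2. Add to the Section 11.4 exceptions that any listed event meeting an SAE criterion is reported on an AE form and sent to the CEC, expressly including serious events suspected to be related to the implant, delivery or TMVR procedure. This also covers serious ventricular tachycardia, which shares an item with VF in Appendix 17.1.5 and raises the same conflict.

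Other brief, non-serious arrhythmias can stay on the list. The edits affect reporting only, not patient care. The cost is a few extra AE forms and CEC reviews, and the reported SAE rate may rise slightly.
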